### **8.1.3. PK and Complement Sample- Day 7 (Select Sites)**

#### **8.1.3.1. Visit 2A—All Groups (Select Sites)**

Blood should be drawn for PK and complement profiling (select sites).

### **8.1.4. Treatment Phase—24 Months**

#### **8.1.4.1. Months 1-12**

##### **8.1.4.1.1. Visits 3-14 (Monthly and Every-Other-Month Groups)**

During this phase, there will be clinic visits every month. Dosing and assessments will occur monthly in the monthly pegcetacoplan and sham injection treatment arms. Dosing will occur EOM in the EOM pegcetacoplan and sham injection treatment arms, however, the subjects will return monthly for assessments (with no dose given).

A complete ophthalmic exam including slitlamp exam of the cornea, iris, anterior chamber, lens, and aqueous reaction (cells and flare), dilated fundus exam of the vitreous and retina, and IOP measurement will be performed and imaging collected as per the Visit Schedule.

Blood will be drawn for safety labs, PK, and complement profile (select sites), Anti-pegcetacoplan antibodies, and genotyping (Month 2 only) prior to the administration of fluorescein as per the Visit Schedule. Samples will be collected for the clinical repository for those subjects that consent to this portion.

Prior to dilating the eyes, all functional tests will be performed (NL-BCVA, LL-BCVA, and MNREAD or Radner Reading Charts [in select countries]). Tests completed using the digital application at select sites (optional) will be completed prior to dilating the eyes but after completion of all functional tests and quality of life measures (NL-BCVA, LL-BCVA, MNREAD or Radner Reading Charts [in select countries], NEI VFQ-25, and FRI). At select sites the subject should be instructed to take the electronic device home and to complete the digital application weekly on the same day each week, if possible. The subject will be instructed to bring back the electronic device for the visits specified in the schedule of events. The quality of life measures (NEI VFQ-25 and FRI) will be administered by the masked site staff.

Imaging will be performed including FAF, FFA, SD-OCT, OCT-A (select sites), endothelial cell count (select sites), and NIR and sent to the reading center for evaluation per the visit schedule.

Study drug or sham injection should be performed by the unmasked physician as described in the MOP and the study eye should be monitored post injection as outlined in [Section 9.15](#). A follow-up phone call should be scheduled with the subject as outlined in the schedule of events.

In the event that a subject is early terminated from the study, all early termination procedures should be performed even if they are outside the allowed study window.

If the subject would like to discontinue dosing but is amenable to continuing in the study, the site should make every effort to have the subject complete as many follow-up visits as possible.

#### **8.1.4.2. Months 13-24**

##### **8.1.4.2.1. Visits 15-26 (Monthly Group) and 15-20 (Every-Other-Month Group)**

During this phase, clinic visits will follow treatment designation (ie, the monthly subjects will return monthly for dosing and assessments and the EOM subjects will return EOM for dosing and assessments). At select sites, subjects will complete the home-based digital assessments weekly during this period.

A complete ophthalmic exam including slitlamp exam of the cornea, iris, anterior chamber, lens, and aqueous reaction (cells and flare), dilated fundus exam of the vitreous and retina, and IOP measurement will be performed and imaging collected per the Visit Schedule.

Blood should be drawn for safety labs, PK, and complement profile (select sites), anti-pegcetacoplan antibodies, and genotyping, prior to the administration of fluorescein as per the Visit Schedule. Samples will be collected for the clinical repository for those subjects that consented to this portion.

Prior to dilating the eyes, all functional tests should be performed (NL-BCVA, LL-BCVA, and MNREAD or Radner Reading Charts [in select countries]). The quality of life measures (NEI VFQ-25 and FRI) should be administered by the masked site staff.

Images should be performed including FAF, FFA, SD-OCT, OCT-A (select sites), endothelial cell count (select sites), and NIR and sent to the reading center for evaluation per the visit schedule.

IVT (or sham) injection should be performed by the unmasked physician as described in the MOP (noting no injections at Month 24) and the study eye should be monitored post injection as outlined in [Section 9.15](#).

In the event that a subject is early terminated from the study, all early termination procedures should be performed even if they are outside the allowed study window.

If the subject would like to discontinue dosing but is amenable to continuing in the study, the site should make every effort to have the subject complete as many follow-up visits as possible.

The completion of the 24-month study period occurs approximately 30 days (monthly treatment group) and approximately 60 days (EOM treatment group) after the last visit at which IP is administered. The period following last dose of IP is sufficient to evaluate the safety of pegcetacoplan based on its half-life in the vitreous; further details can be found in the pegcetacoplan IB. At the end of the 24-month study period, subjects will have the option to enroll into a separate open-label study.

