### Study Design

This is a 24-month, Phase 3, multicenter, randomized, double-masked, sham-injection controlled study to assess the efficacy and safety of multiple IVT injections of pegcetacoplan in subjects with GA secondary to AMD.

The study will randomize approximately 600 subjects across approximately 100 multinational sites. Subjects will be screened within 28 days before receiving pegcetacoplan or sham injection. Upon entry into the study, subjects will be assigned a screening number. Subjects who meet all inclusion and none of the exclusion criteria will return to the clinic for randomization and treatment on Visit 2 (Day 1). At this visit, subjects will be randomized 2:2:1:1 to receive pegcetacoplan monthly (PM), pegcetacoplan every other month (PEOM), sham injection monthly (SM), or sham injection every other month (SEOM), respectively. Randomization will be stratified according to GA lesion area at screening ( $<7.5 \text{ mm}^2$ ;  $\geq 7.5 \text{ mm}^2$ ), and presence of CNV in the fellow eye.

All subjects will be assessed monthly during the first 12 months regardless of treatment regimen. From Month 12 to Month 24, subjects will follow the outlined visit schedule (Appendix A to Appendix D) based on treatment assignment (ie, subjects in the monthly groups will be assessed monthly while subjects in the every-other-month [EOM] group will be assessed EOM). The last visit in the study will be at Month 24, approximately 30 days

(monthly treatment group) or 60 days (EOM treatment group) after the last visit at which investigational product is administered. At the end of the 24-month study period, subjects will have the option to enroll into a separate open-label study.

Subjects who discontinue study treatment, can continue participation in the study and should be encouraged to return to the clinical site for as many follow-up visits as they can (with the exception of pegcetacoplan/sham administration). Subjects who wish to fully withdraw from the study before Month 24, should be encouraged to complete the early termination visit.

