**Table 1: Treatment Arms With Approximate Number of Subjects**

Treatment arms
Pegcetacoplan 15 mg/0.1 mL monthly for 24 months (n = approximately 200 subjects; 24 pegcetacoplan injections)
Pegcetacoplan 15 mg/0.1 mL every other month for 24 months (n = approximately 200 subjects; 12 pegcetacoplan injections)
Sham monthly for 24 months (n = approximately 100 subjects; 24 sham injections)
Sham every other month for 24 months (n = approximately 100 subjects; 12 sham injections)

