## 8. STUDY PROCEDURES

A study schema is presented below in [Figure 1](#). All randomized subjects will return every month to the clinical site for assessments and additional pegcetacoplan or sham injections according to their randomization scheme until Month 12. From Month 12 onwards, subjects will return to the clinical site based on their randomized treatment schedule (monthly or EOM) and will follow the treatment regimen and assessments outlined in the Visit Schedule until Month 24. In addition, subjects will be contacted via phone by masked study staff 4 ( $\pm 2$ ) days after the first 3 study treatments to collect safety information.

The end of this trial for each subject is defined as when the subject completes their Month 24 study visit, approximately 30 days (monthly treatment group) and approximately 60 days (EOM treatment group) after the last visit at which IP is administered. The period following last dose of IP is sufficient to evaluate the safety of pegcetacoplan based on its half-life in the vitreous; further details can be found in the pegcetacoplan IB. At the end of the 24-month study period, subjects will be offered entry to enroll into a separate open-label study.

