### 11.2. Recording Adverse Events

Adverse events and SAEs will be collected from the signing of the consent form until the last visit or early termination visit, 30 days after the last IP administration for the monthly treatment groups and 60 days after the last IP administration for the EOM treatment groups.

Any events that occur prior to dosing will be categorized as pretreatment events; events occurring after dosing will be recorded as TEAEs (start date of dosing and, therefore, categorization of the event will be dependent on randomization assignment).

For each AE, the investigator will evaluate and report the onset date (and time if applicable), resolution date (and time if applicable), intensity, causality, action taken, serious outcome, and whether or not it caused the subject to discontinue the study.

If possible, the outcome of any AE that caused permanent discontinuation or was present at the end of the study should be reported, particularly if the AE was considered by the investigator to be related to the IP. Subjects experiencing AEs that cause interruption or discontinuation of IP, or those experiencing AEs that are present at the last visit or early termination visit should receive follow-up as appropriate.

All SAEs must be reported to the sponsor/Apellis Safety via eCRF within 24 hours of becoming aware of the event, whether or not the event is deemed treatment-related. If the electronic data capture (EDC) system is not operational (or for paper-based study[ies]), the site must complete the paper SAE form and email to CCI immediately and also within 24 hours of becoming aware of the event. The reported information submitted as a paper SAE must be entered into the EDC system once it becomes operational.

Adverse events will be coded in accordance with the Medical Dictionary for Regulatory Activities (MedDRA). If known, the diagnosis of the underlying illness or disorder should be recorded, rather than its individual symptoms.

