**APPENDIX B: VISIT SCHEDULE—Monthly Group—Month 13 to Month 24 (Continued)**

	Treatment												Early Term A	
	Visit #	15	16	17	18	19	20	21	22	23	24	25		26
	Day	390	420	450	480	510	540	570	600	630	660	690		720
	Week	52	56	60	64	68	72	76	80	84	88	92		96
	Month	13	14	15	16	17	18	19	20	21	22	23		24
Window (+ or – days)	8	8	8	8	8	8	8	8	8	8	8	8		
IOP Measurement	x	x	x	x	x	x	x	x	x	x	x	x	x	x
SD-OCT N	x	x	x	x	x	x	x	x	x	x	x	x	x	x
FAF N		SE		SE		x		SE		SE		x	x	
NIR N		SE		SE		x		SE		SE		x	x	
DCFP N												x	x	
FFA N												x	x	
OCT-A R,S						x R						x R	x	
Study Eye Determination														
Randomization														
Pegcetacoplan administration or Sham Injection T	x	x	x	x	x	x	x	x	x	x	x	x		
Postinjection Assessment O	x	x	x	x	x	x	x	x	x	x	x	x		
Follow-Up Call P														
Concomitant Medication/Concomitant Ocular Procedures Q	x	x	x	x	x	x	x	x	x	x	x	x	x	
Adverse Events	x	x	x	x	x	x	x	x	x	x	x	x	x	

Abbreviations: AH50 = alternative pathway of complement functional test; BCVA = best corrected visual acuity; CH50 = classical pathway of complement functional test; CNV = choroidal neovascularization; DCFP = digital color fundus photography; eCRF = electronic case report form; FAF = fundus autofluorescence; FFA = fundus fluorescein angiography; FRI = Functional Reading Independence Index; IOP = intraocular pressure; LL-BCVA = low luminance best corrected visual acuity; MNREAD = Minnesota Low-Vision Reading Test; NEI VFG-25 = National Eye Institute Visual Functioning Questionnaire 25-Item Version; NIR = near infrared reflectance; OCT-A = optical coherence tomography angiography; PK = pharmacokinetics; SD-OCT = spectral domain optical coherence tomography; SE = study eye; Term = termination; VEGF = vascular endothelial growth factor.

Note: All ocular assessments are to be performed for both eyes unless annotated with 'SE' (study eye) in the above schedule. All assessments should be performed on the same day.

All study visits should be scheduled and projected based on the Day 1 visit date with the exception of Visit 2a which should be based on the Day 1 dose date.

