A. For subjects that discontinue the study early, the early termination assessments should be performed after a minimum of 30 days have passed from the last dosing visit. If a subject reports for a scheduled visit and decides to terminate early prior to dosing, the visit should be considered the early termination visit and all early termination procedures should be performed. At Month 24, all subjects should be offered entry into an open-label study.

B. At Day 1 (Visit 2), confirm subject eligibility through reviewing the inclusion/exclusion criteria and receive confirmation of eligibility from the reading center.

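### Do the monthly visit schedules add a 25th injection at Month 24 that the protocol text rules out?

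*Protocol*

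**What the plan says.** The running text gives one consistent account for the monthly arms.

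- Protocol Section 8.1.4.2.1, on the second-year visits: "noting no injections at Month 24".
- Protocol Table 1: "Pegcetacoplan 15 mg/0.1 mL monthly for 24 months (n = approximately 200 subjects; 24 pegcetacoplan injections"; the monthly sham arm also has 24.
- Protocol Synopsis, Study Design: "The last visit in the study will be at Month 24, approximately 30 days" after the last dosing visit in the monthly group. Section 8.1.4.2.1 places study completion "approximately 30 days (monthly treatment group) and approximately 60 days (EOM treatment group) after the last visit at which IP is administered", and Section 8 says the same.
- Protocol Section 11.2 collects adverse events "until the last visit or early termination visit, 30 days after the last IP administration for the monthly treatment groups".
- SAP Section 5.6 plans 24 monthly injections over 24 months (75% of plan is 18 of 24), and its top exposure category is 22-24.

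The other source is the grid of visit schedules. Protocol Section 8 makes it operative: subjects "will follow the treatment regimen and assessments outlined in the Visit Schedule until Month 24". The row at issue is "Pegcetacoplan administration or Sham Injection", with the postinjection assessment row beneath it. It appears in Protocol Appendix B, the COVID-19 version of that table in Appendix K, and SAP Tables 9 and 13.

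**The concern.** In the machine-read text of those four tables, the injection and postinjection rows each carry 12 marks with the Early Term cell blank. There are 12 visits from Month 13 to Month 24, so a literal reading puts an injection at Month 24.

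If that is what is printed, sites have two instructions for the final visit. A site following the grid would treat at a visit with no scheduled in-study follow-up, where the text relies on about 30 days. The two end points for adverse-event collection in Section 11.2 would fall about 30 days apart. A subject with 25 injections would fit no SAP 5.6 category and would count as more than 100% compliant. About 300 subjects (200 pegcetacoplan, 100 sham) are in the monthly arms.

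**Working it through.** **1. The plan's own figure.** SAP 5.6 plans 12 monthly injections before the Month 12 visit and mentions a further one at Month 12, so 12 + 1 = 13 through Month 12. Months 13 to 23 add 11, and 13 + 11 = 24, as in Table 1 and SAP 5.6. The interval agrees: Day 720 − Day 690 = 30 days. The every-other-month arms agree too: 1 + 6 + 5 = 12 injections, and 720 − 660 = 60 days.

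**2. The grid as read.** 13 + 12 = 25. The whole discrepancy is one mark per row.

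**3. Can a mark count in these tables be trusted to within one?** A row filled at every visit and at Early Term should hold 12 + 1 = 13 marks. The urine pregnancy row, blank at Early Term, should hold 12.

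| Row | Table | Expected | Read |
|---|---|---|---|
| IOP, SD-OCT | Protocol Appendix B | 13 | 14 |
| IOP, SD-OCT | SAP Table 9 | 13 | 14 |
| IOP, SD-OCT | SAP Table 13 | 13 | 14 |
| Urine pregnancy | SAP Tables 9 and 13 | 12 | 13 |
| Urine pregnancy | Protocol Appendix B and its Appendix K version | 12 | 12 |

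Surplus marks of exactly one occur in the tables at issue. The urine pregnancy row is read differently in copies of the same schedule.

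**4. Where does the surplus mark go?** Most rows use one symbol throughout and cannot show this. The SD-OCT row of the COVID-19 monthly tables can, because asterisks mark dropped assessments and the symbol changes along the row. The expected pattern is five asterisks (Months 13-17), x (18), five asterisks (19-23), x (24), x (Early Term): 5 + 1 + 5 + 1 + 1 = 13. The vital signs and LL-BCVA rows of the same schedules follow it.

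- SAP Table 13 reads 5, 1, **6**, 1, 1 = 14 marks.
- The Appendix K version reads 5, 1, **6**, 1 = 13 marks, so an asterisk stands in the Month 24 position. The every-other-month counterparts (Appendix K and SAP Table 15) keep an ordinary mark there.

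Months 19 to 23 are five visits, so six asterisks cannot belong to them. On the pages that hold the injection rows, a run ending at Month 23 has been carried one cell too far.

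**5. Applied to the injection row.** A printed row for Months 13 to 23 has 11 marks, and 11 + 1 = 12, exactly what is read. The count of 12 therefore cannot separate a printed Month 24 mark from a reading fault.

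**6. The same row gains marks elsewhere.** Protocol Appendix D, as read, fills every column of the every-other-month injection row, odd months and Month 24 included. SAP Table 11, the same schedule, shows five marks and a blank Month 24. Protocol Appendix C and SAP Tables 10 and 12 show an injection at Early Term; the COVID-19 every-other-month versions (Appendix K, SAP Table 14) do not.

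**7. Size if the mark were printed.** Compliance against the stated plan: 25/24 = 104.2%. Treatment duration by the SAP formula: (690 + 30) − 1 + 1 = 720 days for a last dose on Day 690. For Day 720 it is (720 + 30) − 1 + 1 = 750, truncated at study completion to 720.

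**The case for a change.** The best case for a real contradiction has three parts.

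First, the concomitant medication and adverse event rows, just below the injection rows, read exactly 13 in all four tables, while all eight injection and postinjection rows stop at 12. A fault would have to hit those eight and spare their neighbours. But the faults are row-specific: IOP and SD-OCT overrun on pages where concomitant medication does not, so a clean neighbour proves little. Nor are the eight rows independent. The four tables are copies of one schedule, and IOP and SD-OCT overrun alike in three of them.

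Second, the readable every-other-month grids (Appendix K, SAP Tables 11 and 15) keep Month 24 blank, so the reading process can preserve a blank there. It can, but those rows alternate marks and blanks, unlike a continuous run, and in Protocol Appendix D the blank was lost.

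Third, Section 8 sends sites to the schedule, so a printed mark would be a conflicting instruction about a procedure. That is true, and it is the part that stands: the counts as read are correct, and a printed mark cannot be excluded from this text. It remains a possibility about the printed page, not a demonstrated error.

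The early-termination footnote, "the early termination assessments should be performed after a minimum of 30 days have passed from the last dosing visit", does not help either side. It governs subjects who stop early, not those who complete Month 24.

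**Conclusion.** The concern does not hold. The Synopsis, Sections 8, 8.1.4.2.1 and 11.2, Table 1 and SAP 5.6 agree on the count or on the interval after the last dose: 24 monthly injections, with the final visit about 30 days later. The only contrary evidence is one mark per row in tables whose machine-read text gains a mark per row in other places, including a run that should end at Month 23. Damage of that kind is not an error in the plan.

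This rests on one assumption, that the extra mark is a reading fault. The text supports that explanation without proving it; the printed tables would settle it. If the mark is printed, the schedules and the text would need to be reconciled, and which rule applies is for the sponsor.

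Even then the effect is limited: one missing exposure category, compliance of 104.2% in a group that SAP 5.6 already provides for values above 100%, and no scheduled visit after the last dose. Section 11.5 still provides follow-up for adverse events continuing after study completion. The Month 12 primary analysis, the per-protocol rule, the 18-of-24 threshold, the per-injection event rates, treatment duration (720 days either way) and the SAP 7.1 definition of treatment-emergent events, which sets no end date, are unaffected.

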#### **8.1.5. Early Termination Visit**

A list of all assessments to be performed at the early termination visit can be found on the Visit Schedule. All subjects who end the study early for any reason must complete the early termination visit, however all efforts should be made to have the subject return for as many follow-up visits as possible even if dosing does not occur. All ophthalmic procedures are to be performed on **BOTH EYES**.

#### **8.1.6. Unscheduled Visits**

If a subject returns to the clinical site before their next scheduled visit for an assessment of an AEs or at the request of the physician, all safety assessments should be performed and any additional assessments as deemed medically necessary by the physician.

## **9. ASSESSMENTS**

The following evaluations will be performed during the study as outlined in the Visit Schedule in [Appendix A](#) to [Appendix D](#). Refer to the MOP for detailed descriptions of study-related procedures.

### **9.1. Informed Consent**

Written informed consent for participation must be obtained before performing any study-specific assessments. Informed consent for all subjects should be maintained within the subject source documentation.

### **9.2. Demographic Information/Medical/Surgical History**

Demographic information will be collected from all subjects including but not limited to date of birth, race/ethnicity (where locally permitted). All significant medical conditions and surgeries within the past 5 years should be captured for the subject including chronic and ongoing conditions. Any history or current use of tobacco is to be collected.

### **9.3. Ocular History/Ocular Procedures**

Ocular history within the previous 5 years should be collected and recorded for all subjects. The history should include any significant previous ocular surgeries, procedures and/or medications or treatments used for these conditions.

